8.5.2. Continuous outcome

- LDL-C level (or other lipid measure) closest to 16 weeks between intervention arms.

A linear mixed model with a normal distribution, identity link function will be used with a fixed effect for country and site type (secondary/ tertiary care/mix of both) and a random effect for study site (as a random intercept). We will report adjusted mean difference and 95% confidence interval with p-value. In the case of missing data, multiple imputations will be used to impute the outcome at 16 weeks. Baseline measurements and those taken before 16 weeks will be used for the imputation process

$$y = \beta_0 + \beta_1 ACSDSS_{ij} + \beta_2 COUNTRY1_{ij} + \beta_3 COUNTRY2_{ij} + \beta_4 Site\ type_{ij} + \beta_5 Site\ type_{ij} + \beta_6 BaselineLDL_{ij} + U_j$$

Where:

- y : mean LDL-C (or other lipid measure) in mmol/L
- $ACSDSS_{ij}$: dummy variable for intervention ($ACSDSS_{ij} = 0$ or 1) for patient i in j^{th} site
- $COUNTRY1_{ij}, COUNTRY2_{ij}$: dummy variable for COUNTRY ($COUNTRY_{ij} = 0$ or 1) for patient i in j^{th} site
- $Site\ type1_{ij}, Site\ type2_{ij}$: dummy variable for Site Type ($Site\ type_{ij} = 0$ or 1) for patient i in j^{th} site type
- $BaselineLDL_{ij}$: continuous measure in mmol/L for patient i in j^{th} site
- U_j : random effect for site $j \sim N(0, \sigma_u^2)$

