3.2. Secondary Objectives

1. To compare the time to intensification of LLT in DSS versus routine care.
2. To compare the mean low-density lipoprotein cholesterol (LDL-C) and other key lipid variables by Week 16 in DSS versus routine care.
3. To compare the proportion of patients reaching target LDL-C level (<1.4 mmol/L (<55 mg/dL) by Week 16 in DSS versus routine care.
4. To compare the proportions of patients who receive different types of intensification of LLT: combination therapy by Week 16, escalated monotherapy by Week 16 and escalated combination therapy by Week 16 in DSS versus routine care.

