4.8. Follow Up

Follow-up clinic visits will take place as per routine clinical practice. In general these vary but are expected to occur within 3 months for patients accessing cardiac rehabilitation services or at approximately 12 weeks and 16 weeks post index ACS event after discharge in general (1-2 visits). We have not mandated additional visits and the follow up is intended to reflect routine care pathways although the exact timing may vary (maximum 16 weeks). These visits will consist of standard routine care in both randomised groups, with the exception that at DSS sites, staff will be asked to utilise the DSS to assess whether LLT should be further optimised for consented patients.

Routine clinical care includes blood tests for lipids and blood pressure evaluation, evaluation of lifestyle factors such as smoking, exercise, and diet. In the scenario that a cholesterol measurement is unavailable at the time of follow up, patients will be required to have blood tests after the routine follow up. This situation is not specific to this trial and reflects real world clinical practice.

Every effort will be made to ensure follow up data are collected by sites. Where follow up visits have not been attended by Week 16, sites will access the patient's local medical record and/or contact the patient's GP to determine the outcome data status at Week 16. In the event that the local medical record is not available or the GP does not respond, then the patient will be regarded as lost to follow up from the date of the last visit attended or last known prescription from the patient's record for the purposes of censoring.

Note that, for operational reasons, some patients may have data reported at 24 weeks only. These data may be used, where appropriate, to derive or impute the LLT medication status at 16 weeks.

The schedule of events is shown in **Error! Reference source not found..**

Table 1: Schedule of Time and Events

	Baseline	All other visits as per routine care up to 16 weeks
Visit	1	2 onwards
Informed consent	X	
Inclusion & exclusion criteria	X	X
DSS variables	X	X ^a
Demography	X	
CV Medical history	X	
Vital Signs ^b	X	X
Full Lipid Profile	X	X
Medications / LLT	X	X
Lifestyle (smoking, exercise & diet)	X	X
CV events	X	X

^a DSS use optional after Baseline visit

^b Includes height, weight, body mass index, temperature, diastolic and systolic blood pressure, and blood pressure position

5. Variables of Analysis

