5.3. Secondary Efficacy Variables

1. Time to intensification of LLT by week 16
2. LDL-C level closest to 16 weeks
3. Non-HDL-C level closest to 16 weeks
4. HDL-C level closest to 16 weeks
5. TC level closest to 16 weeks
6. Triglycerides level closest to 16 weeks
7. Proportion of patients' reaching target LDL-C levels, <1.4 mmol/L (<55 mg/dL) by week 16
8. Proportion of patients who receive combination therapy by Week 16
9. Proportion of patients who receive escalated monotherapy by Week 16
10. Proportion of patients who receive escalated combination therapy by Week 16

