We define the primary outcome as missing for anyone who does not have full 16 week follow up, unless they have met the primary outcome prior to the time they are lost to follow up. All patients will be followed up and the primary outcome data will be collected unless the participant requests to withdraw from data collection. Missing data will be examined and quantified; this will include the time of withdrawal and tabulation for reasons for non-completion of study by country, site, and arms. Patterns of missingness and relationship between variables and outcome will be explored. The proportion of clusters (sites) with a missing individual outcome will be calculated and reported as the number of entire clusters with a missing outcome divided by the number of clusters randomised.

As mentioned in Section 4.8, some patients may have data reported at 24 weeks only. These data may be used, where appropriate, to derive or impute the LLT medication status at 16 weeks.

Although mixed models are valid under the missing at random (MAR) assumption, we will use the multilevel multiple imputation (MMI) method to impute values for individuals who have missing outcome data. Missing data can be related to the cluster level or at patient level. We define level 1 variables as those relating to the patient as X and Y and Z, and level 2 variables as those relating to the site as A and B.

Using the *JOMO package* in R with missing outcome data we can use an imputation model which is the same as the analysis model. The JOMO package allows imputation on a mix of multilevel continuous and categorical data.¹⁵ This method uses Markov chain Monte Carlo (MCMC) methods to impute missing values. We will run N imputations and combine the estimates using the mitools package. We will impute N datasets based on the percentage of participants with incomplete outcomes, where N is rounded to the nearest 10. A minimum of 5 imputation datasets will be used. We will include at patient level, intervention, outcome,

Imperial Clinical Trials Unit	ZODIAC STATISTICAL ANALYSIS PLAN – MAIN ANALYSIS	V1 17 th Jan 2024
-------------------------------	--	------------------------------

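### SAP 8.5.2 does not name post-admission LLT among the inputs for imputing missing week-16 lipids; the LDL-C difference is biased if having a lipid value depends on LLT

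*SAP*

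**What the plan says.** The secondary objective (SAP 3.2) is "To compare the mean low-density lipoprotein cholesterol (LDL-C) and other key lipid variables by Week 16 in DSS versus routine care". The variable (SAP 5.3) is "LDL-C level closest to 16 weeks", and likewise for the other lipids, with no time window.

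SAP 8.5.2 gives the analysis: a linear mixed model with arm, country, site type, baseline value and a random site intercept. On missing values it says "In the case of missing data, multiple imputations will be used to impute the outcome at 16 weeks", followed by "Baseline measurements and those taken before 16 weeks will be used for the imputation process". Nothing else in the SAP specifies the lipid imputation. The predictor list in 8.4 is for the binary primary outcome and holds no LLT regimen. The example code in 14.3 has placeholder covariates.

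On what is known about LLT:

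- The schedule in SAP 4.8 lists "Medications / LLT" at baseline and at all later routine visits. SAP 5.2 compares forms completed before admission, at discharge and at follow-up, and Table 17 reports LLT at discharge.
- For non-attenders, SAP 4.8 says "Where follow up visits have not been attended by Week 16, sites will access the patient's local medical record and/or contact the patient's GP". The purpose is to establish outcome status.
- For patients with 24-week data only, SAP 8.4 says "These data may be used, where appropriate, to derive or impute the LLT medication status at 16 weeks". No matching provision is stated for lipids.
- SAP 4.8 also has a safeguard, with the test falling later than the routine visit: "In the scenario that a cholesterol measurement is unavailable at the time of follow up, patients will be required to have blood tests".

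**The concern.** The DSS informs a prescribing decision (SAP 4.2), so it can move LDL-C only through LLT. An imputation that ignores LLT assumes that, given arm and earlier lipids, patients with and without a week-16 value have the same LDL-C distribution. That fails if the two groups differ in LLT.

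SAP 8.3 defines the baseline lipid as the last value on or before the day of admission, so it predates any treatment change made for the index event. For a patient with no later lipid, the named inputs therefore contain nothing about what was prescribed at discharge or afterwards, even when the forms record it. An interim lipid carries that information only if it was drawn after the change.

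At stake are the adjusted mean differences for LDL-C, non-HDL-C and total cholesterol, which are reported with confidence intervals and p-values. Table 26 reserves a count for missing lipid values, so the plan expects some.

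**Working it through.** **The plan's own figures.** The documents state no figure for lipid missingness or for the lipid effect. The only related figures are in SAP 4.5, and they reproduce. The design effect is 1 + (31 − 1) × 0.1 = 4.0. The unpooled two-proportion size for 0.05 versus 0.15 is 183.9 per arm, and 183.9 × 4 = 735.5, or 23.7 clusters of 31. That rounds to 24 × 31 = 744. Allowing for 5% loss, 744/0.95 gives 784 per arm, or 1568.

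**Inputs**

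- Intensified: 5% SoC, 15% DSS. SAP 4.5 states these for combination therapy, which is narrower than the intensification outcome, so using them here is an assumption.
- d = 0.8 mmol/L, the LDL-C fall from intensification: assumed.
- m, the fraction without a week-16 lipid: assumed 5% to 30%.
- f, the intensified share among unmeasured patients relative to measured patients: assumed 0, 0.5 or 1.

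**Formula.** If p is the intensified share in an arm, p = (1 − m)·p_obs + m·f·p_obs, so p_obs = p / [(1 − m) + m·f]. Imputing within arm from baseline gives unmeasured patients the mean of measured ones. The estimate is then −d × (p_obs in DSS − p_obs in SoC). The true effect is −0.8 × (0.15 − 0.05) = −0.080 mmol/L. With equal m and f in both arms, the estimate is the true effect divided by (1 − m) + m·f, whatever d is.

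| m, both arms | f = 0 | f = 0.5 | f = 1 |
|---|---|---|---|
| 5% | ÷0.95: −0.084 (+5.3%) | ÷0.975: −0.082 (+2.6%) | −0.080 (0) |
| 10% | ÷0.90: −0.089 (+11.1%) | ÷0.95: −0.084 (+5.3%) | −0.080 (0) |
| 20% | ÷0.80: −0.100 (+25.0%) | ÷0.90: −0.089 (+11.1%) | −0.080 (0) |
| 30% | ÷0.70: −0.114 (+42.9%) | ÷0.85: −0.094 (+17.6%) | −0.080 (0) |

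**Direction.** If f exceeds 1 the divisor exceeds 1 and the effect is diluted. Unequal missingness can also turn the sign of the bias. With illustrative rates of 40% versus 50% and f = 0:

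- SoC 20% missing, DSS 10%: 0.50/0.90 − 0.40/0.80 = 0.0556, an estimate of −0.044 (bias +0.036).
- SoC 10% missing, DSS 20%: 0.50/0.80 − 0.40/0.90 = 0.1806, an estimate of −0.144 (bias −0.064).

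**No true effect.** Equal missingness gives no bias. With 40% intensified in both arms, f = 0.5, and 20% (SoC) versus 10% (DSS) missing, the shares are 0.40/0.90 = 0.444 and 0.40/0.95 = 0.421, a bias of 0.8 × 0.023 = +0.019 mmol/L.

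**Does adding LLT help?** Simulation check: 48 sites of 33, 400 runs, 10 imputations, 5% versus 15%, f = 0, with LLT as a yes/no state and no site effect in the imputation. Shift from the full-data estimate, in mmol/L:

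| Scenario | LLT not in imputation | LLT in imputation |
|---|---|---|
| 5% missing | −0.004 | within 0.001 of zero |
| 20% missing | −0.022 | −0.002 |
| 30% missing | −0.034 | 0.000 |
| 20% missing, informative interim lipid used | −0.015 | 0.000 |

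Except in the last row, the imputation used arm and baseline only, which is weaker than the plan, since the plan also uses lipids taken before week 16.

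**The case against.** The case for leaving the text alone has real force.

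- A reader might infer that the SAP restricts the imputation to lipid values and excludes LLT. It does not say so. The sentence in 8.5.2 is not worded as exclusive, does not define measurements, and does not name arm or site either. This stands. But even a broad reading of baseline data brings in only LLT before admission (SAP 5.1), and no text names LLT after admission. If the sentence is not a full list, the model is unspecified and needs the same edit.
- A reader might also infer that unmeasured patients are mostly known not to have been intensified. The documents do not support this. Under SAP 5.2, intensification can occur by discharge, before any follow-up visit, and Table 1 makes DSS use optional after baseline.
- Missing lipids may be few. Sites must be able to supply blood tests (SAP 4.4.1), a test is required when a value is unavailable, the record or GP search is for outcome data and may yield lipids, and the outcome has no window. All this can lower missingness. It does not cover a patient with no post-baseline lipid at all, whose LLT may still be on record.
- The 5% loss in SAP 4.5 suggests a small effect. That rate rests on patients asking for data collection to stop and is not a lipid rate.
- SAP 9.2 calls the secondary results hypothesis-generating. This limits the weight of the point.

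**Conclusion.** The point holds as a conditional weakness with a cheap remedy. The lipid imputation as written does not name post-admission LLT, which lies on the path from the DSS to LDL-C and can be known when the lipid is missing. The adjusted mean differences for LDL-C, non-HDL-C and total cholesterol are biased if having a lipid value depends on LLT given arm and earlier lipids. They are not biased by this route otherwise.

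At equal missingness, 5% versus 15% intensified and no unmeasured patient intensified, the exaggeration is about 5% at 5% missing (−0.084 against −0.080 mmol/L) and 25% at 20% missing (−0.100 against −0.080). The mmol/L figures also rest on d = 0.8. The bias is smaller when interim lipids are informative. Larger or opposite-signed bias needs more missingness, or missingness that differs between arms, and the documents report neither.

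The stronger conclusion, that the planned LDL-C comparison is biased in a known direction, is not supported.

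**What to change.** In SAP 8.5.2, replace the sentence on imputation inputs with a full predictor list for the lipid outcomes:

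- arm, site, country and site type;
- baseline and interim lipids;
- LLT regimen or intensity at discharge and at the last follow-up up to week 16, so that starting monotherapy in an LLT-naïve patient is captured (under SAP 5.2 this does not count as intensification, though LDL-C is expected to fall);
- the intensification class from SAP 5.2 and Appendix A.

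State that LLT enters the imputation only. The analysis model stays as it is, because adjusting for LLT would remove the effect that the trial is estimating. Tabulating lipid missingness by arm and LLT status would show whether the condition for bias is met.

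The cost is a sentence or two in the SAP and extra columns in the imputation call. There are two downsides. Intensity categories are tabulated only before admission and at discharge (Tables 16 and 17), so the week-16 category must be derived from the follow-up forms. Patients missing both LLT and lipids need the two imputed jointly; SAP 8.4 notes that the chosen package handles mixed continuous and categorical multilevel data.

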8.5.3. Binary outcomes

- Proportion of patients' reaching target LDL-C levels, <1.4 mmol/L (<55 mg/dL) by Week 16, proportion of patients who receive combination therapy, proportion of patients who receive escalated monotherapy and proportion of patients who receive escalated combination therapy

This analysis will be for all people with Week 16 follow-up.

We will follow the same approach as described for primary outcome and use log-binomial model or modified Poisson regression with a fixed effect for country and site type (secondary/ tertiary care/mix of both) and a random effect for study site (as a random intercept) to estimate an adjusted Risk Ratio with a 95% confidence interval and p-value.

Imperial Clinical Trials Unit	ZODIAC STATISTICAL ANALYSIS PLAN – MAIN ANALYSIS	V1 17 th Jan 2024
-------------------------------	--	------------------------------

Model assumptions for all models will be examined using residual analysis. Following the recommendations by Parker¹⁶ and Rubin¹⁷ no adjustments for multiple testing will be used but a precise, focused interpretation of the individual results for secondary outcomes will be reported.

$$\log(\pi_{ij}) = \beta_0 + \beta_1 ACSDSS_{ij} + \beta_2 COUNTRY1_{ij} + \beta_3 COUNTRY2_{ij} + \beta_4 Site\ type_{ij} + \beta_5 Site\ type_{ij} + U_j$$

Where:

- π_{ij} : probability of combination therapy (or other binary outcome) for the i^{th} patient in j^{th} site
- $ACSDSS_{ij}$: dummy variable for intervention ($ACSDSS_{ij} = 0$ or 1) for patient i in j^{th} site
- $COUNTRY1_{ij}, COUNTRY2_{ij}$: dummy variable for COUNTRY ($COUNTRY_{ij} = 0$ or 1) for patient i in j^{th} site
- $Site\ type1_{ij}, Site\ type2_{ij}$: dummy variable for Site Type ($Site\ type_{ij} = 0$ or 1) for patient i in j^{th} site type
- U_j : random effect for site $j \sim N(0, \sigma_u^2)$

8.6. Safety Analysis

Information on adverse device effects (ADEs) that are considered to be definitely related to the DSS will be collected. These ADEs will be tabulated for the DSS arm only and stratified by severity. Data will be presented as the number of patients with at least one ADE, and as the number of ADEs reported.

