5.4. Safety Variables

This trial is using the DSS system that is classified as a device. Therefore we will provide safety reporting on the following for the DSS arm only:

1. Adverse Device Effects (ADE): Any untoward and unintended response to a medical device.
 - This definition includes any event resulting from insufficiencies or inadequacies in the instructions for use or the deployment of the device.
2. Serious Adverse Device Effects (SADE): Adverse device effect that has resulted in any of the consequences characteristic of a serious adverse event or that might have led to any of these consequences if suitable action had not been taken or intervention had not been made or if circumstances had been less opportune.
 - Unanticipated Serious Adverse Device Effect (USADE): Any serious adverse device effect which, by its nature, incidence, severity or outcome, has not been identified in the anticipated AE's
 - Anticipated Serious Adverse Device Effects (ASADE): is an effect which by its nature, incidence, severity or outcome has been identified in the anticipated AE's. No ASADEs have been identified in this case.

Imperial Clinical Trials Unit	ZODIAC STATISTICAL ANALYSIS PLAN – MAIN ANALYSIS	V1 17 th Jan 2024
-------------------------------	--	------------------------------

The assignment of causality and severity for adverse device effects should be made by the investigator responsible for the care of the patient using the definitions in the tables below (**Error! Reference source not found.** and **Error! Reference source not found.**).

Table 3: Causality definitions of adverse device effects

Causality	Definition
Unrelated	No evidence of any causal relationship
Unlikely	There is little evidence to suggest there is a causal relationship (e.g. the effect did not occur within a reasonable time after use of the device . There is another reasonable explanation for the effect(e.g. the patient's clinical condition, other concomitant treatment).
Possible	There is some evidence to suggest a causal relationship (e.g. because the effect occurs within a reasonable time after use of the device). However, the influence of other factors may have contributed to the effect (e.g. the patient's clinical condition, other concomitant treatments).
Probable	There is evidence to suggest a causal relationship and the influence of other factors is unlikely.

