7.2. Safety Population

As in this trial all patients will be treated only in line with SoC, the treating physicians at study sites will report any Adverse Drug Reactions (ADRs)/ Adverse Events (AEs) in routine ways in accordance with the guideline on Good Pharmacovigilance Practice (GVP) for all medications trial patients are taking during the course of the trial. This is not a Clinical Trials of Investigational Medicinal Product (CTIMP), therefore no Serious Adverse Events in relation to the licensed medicines are being collected.

Device deficiencies will be captured in those patients who are at a study site using DSS only. Device deficiencies include malfunctions, user errors and inadequacy in the software supplied by the manufacturer.

Imperial Clinical Trials Unit	ZODIAC STATISTICAL ANALYSIS PLAN – MAIN ANALYSIS	V1 17 th Jan 2024
-------------------------------	--	------------------------------

8. Statistical Analysis

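### SAP 8.6 limits adverse device effects to those judged definitely related, in conflict with SAP 5.4 and Table 33, so effects graded possible or probable could go unreported

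*SAP*

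**What the plan says.** SAP 5.4 treats the decision support system (DSS) as a device and plans safety reporting of ADEs and serious ADEs (SADEs) in the DSS arm. It defines an ADE as "Any untoward and unintended response to a medical device", extends this to problems arising from the instructions or deployment, and sets no minimum causality grade. It adds that "The assignment of causality and severity for adverse device effects should be made by the investigator responsible for the care of the patient", using Table 3 for causality (Unrelated, Unlikely, Possible, Probable, Definite) and Table 4 for severity.

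SAP 8.6 is narrower. It says that "Information on adverse device effects (ADEs) that are considered to be definitely related to the DSS will be collected" and then that "These ADEs will be tabulated for the DSS arm only and stratified by severity".

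The output shells are Table 31 (ADE, SADE, and SADEs split into unanticipated and anticipated), Table 32 (severity), Table 33 (ADE; Related; Serious and Related; Serious, Related and Unanticipated) and Table 34 (system organ class and preferred term). No section says which causality grades count as Related.

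SAP 7.2 also has device deficiencies captured at DSS sites: "Device deficiencies include malfunctions, user errors and inadequacy in the software supplied by the manufacturer". Section 8.6 and Tables 31 to 34 do not report them.

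**The concern.** The restriction in 8.6 falls on what is collected as well as on what is displayed. A display rule can be changed at analysis, but an event that a site was never asked to record cannot be recovered then.

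The restriction also sits at the most demanding grade. Table 3 reserves Definite for effects where other contributors can be excluded. By SAP 4.2 the tool does not itself recommend treatment, and the prescribing decision stays with the clinician. A patient-level effect of the tool would therefore normally act through a prescribing decision in someone with a recent acute coronary syndrome. Excluding other contributors is a demanding test in that setting. This is an inference from the SAP's description of the device; the documents give no figure for it.

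What is at stake is the meaning of the device-safety statement at the end of the trial. A low ADE count could mean that the tool caused few problems, or only that few problems met the strictest grade. The primary efficacy result is not affected.

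**Working it through.** No arithmetic applies: the safety sections state no rate, count or threshold to reproduce. The check sets the sections side by side.

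**Step 1. Causality grades under each section.**

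| Grade (Table 3) | Evidence of causation according to the SAP | Reportable under 5.4 | Collected under 8.6 |
|---|---|---|---|
| Unrelated | none | no grade excluded | no |
| Unlikely | little | no grade excluded | no |
| Possible | "There is some evidence to suggest a causal relationship (e.g. because the effect occurs within a reasonable time after use of the device" | yes | no |
| Probable | "There is evidence to suggest a causal relationship and the influence of other factors is unlikely" | yes | no |
| Definite | clear, with other contributors excluded | yes | yes |

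One grade of five passes 8.6. Of the three grades where the scale points towards causation (Possible, Probable, Definite), 8.6 drops two. This counts categories, not events.

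**Step 2. What Table 33 would show if 8.6 were followed.** Every collected ADE would be Definite, so:

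- Related would equal the ADE total, under any definition of Related that includes Definite.
- Serious and Related would equal the SADE row of Table 31.
- Serious, Related and Unanticipated would equal the unanticipated-SADE row of Table 31. SAP 5.4 identifies no anticipated serious effects, so this would also equal the SADE row.

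Table 33 would then repeat Table 31 and add nothing. The shell is informative only if ADEs below Definite are also collected.

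**Step 3. What still gets through.** Causality and seriousness are separate classifications. A serious or unanticipated effect graded Definite passes the limit and appears in Tables 31, 33 and 34. A serious effect graded Probable does not.

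**Step 4. Other sources of harm data.**

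- All-cause and cardiovascular mortality and cardiovascular events are described by arm with no causality filter (SAP 5.5, 8.4 and Table 35).
- Non-completion because of death or an adverse event is tabulated by arm (Table 21).
- Drug reactions go through routine pharmacovigilance; serious events related to the licensed medicines are not collected in the trial (SAP 7.2).
- Device deficiencies are captured (SAP 7.2) but have no planned output.

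None of these reports an event as an effect of the tool graded Possible or Probable.

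**Step 5. TEC reports.** SAP 8.7 lists adverse device events in the closed reports and sets no causality limit. However, a report can contain only what was collected. If 8.6 governs collection, the limit carries through to the TEC.

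**The case against.** The best defence is that 8.6 is loosely worded and wider collection was intended. Section 5.4, the separate Related row in Table 33 and the unrestricted wording in 8.7 all point that way. Grading on five levels and then reporting one is also coherent in itself, because the scale is what identifies Definite. And what sites record would normally be set by the protocol's safety section and the eCRF. Neither was in the text available for this review, so actual collection could not be checked.

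Most of this stands. It shows that the SAP is unresolved, not that 8.6 is harmless. The word about collection in 8.6 is explicit, and nothing in the SAP says that 5.4 takes precedence.

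A reader might infer four stronger things that the documents do not support:

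- **That all safety data are limited to Definite effects.** The limit applies to ADE reporting. Deaths and cardiovascular events are described by arm without any causality judgement, and a comparison of that kind can pick up harm acting through prescribing.
- **That the tables would be empty or the count near zero by construction.** Definite effects are counted, including serious and unanticipated ones, and no ADE rate or split by grade is given.
- **That Possible and Probable effects are certain to be lost.** That follows only if 8.6 governs. If 5.4 governs, they could be reported.
- **That the plan withholds such effects from the TEC.** Section 8.7 contains no such rule; the gap would come only from non-collection.

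**Conclusion.** The conflict within the SAP is real and should be resolved. If 8.6 is followed as written, ADEs graded Possible or Probable, including serious ones, are neither collected nor shown in Tables 31 to 34, and so cannot appear in the TEC reports. These are effects for which the SAP's own scale acknowledges evidence of a causal link.

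The size can be stated only in grades: four of the five fall outside the limit, two of which carry some evidence of causation. The number of events cannot be estimated from the documents.

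The conclusion rests on one assumption: that the 8.6 sentence, rather than 5.4 or the protocol and eCRF, determines what sites record. If collection is already wider, the remaining defects are an incorrect sentence in 8.6, an undefined Related category in Table 33, and device deficiencies that are captured but not reported.

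**What to change.** 1. Remove the restriction to definitely related effects from 8.6, so that it agrees with 5.4.
2. Tabulate all reported ADEs in Tables 31 to 34 by causality grade, severity and seriousness.
3. Define Related by grade, for example Possible, Probable or Definite. The SAP sets no cut-off, so the trial team must choose one and state it.
4. Use the same definition in the TEC reports under 8.7.
5. Check that the protocol safety section, the eCRF and the site instructions match. If collection really is restricted, SAP wording alone cannot recover the missing events and those documents must change too.
6. Add a listing of the device deficiencies already captured under 7.2.

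The causality scale already exists, so the SAP change is a few sentences and a few table rows. The other costs are somewhat more reporting by sites and, if collection is in fact restricted, revised eCRF or site-instruction wording. If collection is already wide, correcting 8.6 itself takes one sentence.
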